9.0 ADVERSE EVENT, ADVERSE DEVICE EFFECT, DEVICE DEFICIENCY

9.1 DEFINITIONS

9.1.1 Adverse Event (AE)

Any untoward medical occurrence, unintended disease or injury, or untoward clinical signs (including abnormal laboratory findings) in subjects, users or other persons, whether or not related to the investigational medical device under study.

This definition includes events related to the investigational medical device or the comparator.

This definition includes events related to the procedures involved.

9.1.2 Serious Adverse Event (SAE)

An adverse event that led to:

- Death
- A serious deterioration in the health of the subject, that either resulted in:
 - A life-threatening illness or injury OR
 - A permanent impairment to a body structure or a body function OR
 - An in-patient or prolonged hospitalization OR
 - A medical or surgical intervention to prevent life-threatening illness or injury or permanent impairment to a body structure or a body OR

Clinical Investigational Plan

- Fetal distress, fetal death or a congenital abnormality or birth defect
A planned hospitalization for a pre-existing condition, or a procedure required by the CIP is not considered a serious adverse event.

9.1.3 Adverse Device Effect (ADE)

An adverse event related to the use of the device.

This definition includes adverse events resulting from insufficient or inadequate instructions for use, deployment, implantation, installation, or operation, or any malfunction of the investigational medical device.

This definition includes any event resulting from the use error or from intentional misuse of the investigational medical device.

9.1.4 Serious Adverse Device Effect (SADE)

Adverse device effect that has resulted in any of the consequences characteristic of a serious adverse event.

9.2 PROCEDURE FOR ASSESSING, RECORDING, AND REPORTING ADVERSE EVENTS

Safety surveillance within this study and the safety reporting performed both by the investigator and Sponsor starts as soon as the procedure begins, which is defined as the time the dilator/device delivery system has been introduced into the body. The safety surveillance and the safety reporting will continue until the last visit has been performed, the subject is deceased, the subject/investigator concludes his participation into the study or the subject/investigator withdraws the subject from the study.

For the purposes of this study, the following AEs will be collected:

- All AEs (regardless of seriousness)
- All SAEs (regardless of relatedness)
- In addition, the following event types will also be reported
- device embolization, device erosion, clinically significant device interference with surrounding structure, device thrombus, device fracture, device infection (endocarditis / pericarditis), device perforation, device laceration, or device allergy

All AE data will be collected throughout the clinical study and will be reported to the Sponsor through the EDC system. The Investigator will record all AE on the appropriate eCRF as soon as possible, but no later than 5 working days of first learning of the event.

For any SAE (including deaths) and any SADE, the investigator shall notify the Sponsor through the EDC system immediately (but no later than 3 working days) of the investigator's awareness of the event and provide the Sponsor with all necessary documentation needed. The Sponsor will notify relevant regulatory authorities and all the other participating sites no later than 5 working days after awareness of the event.

Clinical Investigational Plan

The investigator and Institution will report SAE (including deaths) and SADE to the IRB/EC / relevant regulatory authorities no later than 24 hours of first learning of the event per CFDA's regulations.

Records relating to the subject's subsequent medical course must be maintained and submitted (as applicable) to the Sponsor until the event has subsided or, in case of permanent impairment, until the event stabilizes and the overall clinical outcome has been ascertained. Additional information may be requested, when required, by the Sponsor in order to support the reporting of AEs to regulatory authorities.

Adverse events will be monitored by the investigator until they are adequately resolved. The status of the subject's condition should be documented at each follow-up visit.

All adverse events will be reported as per applicable regulatory requirements.

9.3 SUBJECT DEATH

9.3.1 Procedure for recording and reporting subject death

All subject deaths with all necessary documentation needed are to be reported to the Sponsor immediately upon the investigator's awareness of the event. An Adverse Event eCRF should be completed and include additional detail surrounding the death and cause of death. The principal investigator should also record any observed device deficiencies, that may be applicable.

9.4 DEVICE DEFICIENCY (DD)/COMPLAINTS

A Device Deficiency is defined as an inadequacy of a medical device with respect to its identity, quality, durability, reliability, safety or performance.

Device deficiencies include malfunctions, use errors, and inadequate labeling.

Device deficiencies will be reported per country reporting timeline requirements to the Sponsor and are recorded outside of the study database through the EPIQ Complaint system or on a Product Event Report Form.

If the device deficiency involves an adverse event as described in the protocol, the Investigator shall notify the Sponsor by completing the AE form through EDC as applicable and must provide the Sponsor with all necessary documentation needed.

If the device deficiency does not involve a reportable AE per protocol, the Investigator should notify the SJM Product Surveillance Department by submitting the information about the device deficiency to the local country office or to: [contact] or calling [contact] as soon as possible after becoming aware of the device deficiency. Please contact the local SJM representative to coordinate product returns as applicable.

10.0 DATA MANAGEMENT

Overall, the Sponsor will be responsible for the data handling.

The sponsor and/or its affiliates will be responsible for compiling and submitting all required reports to governmental agencies.

Clinical Investigational Plan

Data will be analyzed by the Sponsor and may be transferred to the Sponsor's locations outside of China and/or any other worldwide regulatory authority in support of a market-approval application.

St. Jude Medical respects and protects personally identifiable information collected or maintained for this clinical investigation. The privacy of each subject and confidentiality of his/her information will be preserved in reports and when publishing any data. Confidentiality of data will be observed by all parties involved at all times throughout the clinical study. All data will be secured against unauthorized access.

Electronic CRFs will be used in this study, as noted below and in the data management plan. Informed consent documents will be translated to Chinese, as applicable. If additional documentation is required for any reason (e.g. procedural notes for an adverse event), it is to be appropriately redacted/de-identified prior to being sent to SJM. Source documents will be collected and translated, as needed, for reporting, etc.

The Principal Investigator or institution will provide direct access to source data during and after the clinical study for monitoring, audits, IRB/EC review and regulatory authority inspections. As required, the Principal Investigator or institution will obtain permission for direct access to source documents from the subject, hospital administration and national regulatory authorities before starting the clinical study.

10.1 DATA MANAGEMENT PLAN

A detailed Data Management Plan will be established to ensure consistency of the data. This document will include procedures used for data review, database cleaning, and issuing and resolving data queries. If appropriate, the DMP may be updated throughout the study duration. All revisions will be tracked and document controlled.

CRF data will be captured in a validated electronic database management system hosted by St. Jude Medical. Only authorized site personnel will be permitted to enter the CRF data through the electronic data capture (EDC) system deployed by St. Jude Medical. An electronic audit trail will be used to track any subsequent changes of the entered data.

10.2 DOCUMENT AND DATA CONTROL

10.2.1 Traceability of documents and data

The investigator will ensure accuracy, completeness, legibility and timeliness of the data reported to the sponsor on the CRFs and in all required reports.

10.2.2 Recording data

Source documents will be created and maintained by the investigational site team throughout the clinical study.

The data reported on the eCRFs will be derived from, and be consistent with, these source documents, and any discrepancies will be explained in writing.

The CRFs will be signed and dated (validated eCRF) by the authorized site personnel, as specified in the Data Management Plan.

Clinical Investigational Plan

11.0 MONITORING

It is the responsibility of St. Jude Medical as the sponsor of the study to ensure the study is conducted, recorded, and reported according to the approved protocol, subsequent amendment(s), applicable regulations, and guidance documents. Monitoring will be conducted according to the St. Jude Medical Clinical Monitoring standard operating procedure.

Prior to beginning the study, St. Jude Medical will contact the investigator or designee to discuss the study and data requirements. A St. Jude Medical monitor will periodically review the subject records and associated source documents.

The investigator shall make subject and study records available to the clinical monitor for monitoring.

12.0 REGULATORY INSPECTIONS

The investigator and/or delegate should contact St. Jude Medical immediately upon notification of a governmental agency inspection at the site. A clinical monitor or designee will assist the investigator and/or delegate in preparing for the audit.

An investigator who has authority to grant access will permit authorized governmental agency employees, at reasonable times and in reasonable manner, to enter and inspect any establishment where devices are held (including any establishment where devices are used or where records or results are kept).

An investigator, or any person acting on behalf of such a person with respect to the study, will permit authorized governmental agency employees, at reasonable times and in reasonable manner, to inspect and copy all records relating to the study.

An investigator will permit authorized governmental agency employees to inspect and copy records that identify subjects, upon notice that governmental agency has reason to suspect that adequate informed consent was not obtained, or that reports required to be submitted by the investigator, to the Sponsor or IRB/EC have not been submitted or are incomplete, inaccurate, false or misleading.

13.0 STATISTICAL CONSIDERATIONS

13.1 PRIMARY ENDPOINTS

There are three primary endpoints: two safety endpoints and one effectiveness endpoint.

13.1.1 Primary safety endpoint (Short Term)

The short term safety endpoint is the proportion of subjects who experience an major adverse events (short term occurrence of death, stroke (ischemic or haemorrhagic), systemic embolism, or procedure or device-related complications requiring major cardiovascular or endovascular intervention) 7 days after the procedure.

Hypothesis:

$$H_0: p_s \geq PG_s$$

$$H_1: p_s < PG_s$$

Clinical Investigational Plan

where p_s is the proportion of subjects undergoing the ACP LAA closure procedure, who experience an acute safety endpoint event. [REDACTED]

[REDACTED]

[REDACTED]

The performance goal, PG_s , in this hypothesis is set at 10%.

[REDACTED]

[REDACTED]

[REDACTED]

[REDACTED]

[REDACTED]

[REDACTED]

[REDACTED]

[REDACTED]

[REDACTED]

Analysis Methods:

The proportion of subjects experiencing a primary safety endpoint, p_s , will be estimated from the binomial model. [REDACTED]

[REDACTED]

[REDACTED]

[REDACTED]

The performance goal assumes that LAA closure occurs in isolation of other cardiac procedures. If the short-term primary safety endpoint is not met, then an additional analysis may be performed excluding subjects who had a cardiac ablation performed in combination with the ACP LAA closure procedure. Excluding subjects who had a cardiac ablation performed in combination with the LAA closure procedure may result in a substantially smaller sample size to evaluate this endpoint; therefore, in this additional analysis, the point estimate for the short-term primary safety endpoint will be descriptively compared to the performance goal, PG_s .

Sample Size Determination:

Sample sizes are calculated assuming an event rate of 5%. The sample size required to reject the null hypothesis with 80% power at the 2.5% significance level is 231 subjects.

Analysis Population:

Enrolled subjects will be included in this analysis.

13.1.2 Primary safety endpoint (Long-Term)

The long-term safety endpoint is the 2-year occurrence of device embolization, device erosion, clinically significant device interference with surrounding structure, device thrombus, device fracture, device infection (endocarditis / pericarditis), device perforation, device laceration, or device allergy.

[REDACTED]

[REDACTED]

Clinical Investigational Plan

Hypothesis:

$$H_0: p_l \geq PG_l$$

$$H_1: p_l < PG_l$$

where p_l is the long-term safety endpoint event rate. It is assumed that the long-term safety endpoint event rate is 5%. [REDACTED]

[REDACTED]

[REDACTED]

[REDACTED] An event rate of 5% is assumed for the long-term safety endpoint for the ACP device [REDACTED]

[REDACTED] The performance goal, PG_l , is set at 10% [REDACTED]

[REDACTED]

[REDACTED]

[REDACTED]

Analysis Methods:

Kaplan-Meier survival analysis will be used to estimate the event rate of at 24 months (731 days post implant). [REDACTED]

[REDACTED]

Sample Size Determination:

The sample size is estimated assuming an event rate of 5%. A sample size of 231 subjects followed through 24 months will provide 80% power at the 2.5% significance level. Assuming an attrition rate of 25% through 24 months, 308 subjects are required to be enrolled in the study.

Analysis Population:

Enrolled subjects will be included in this analysis.

13.1.3 Primary effectiveness endpoint:

The primary effectiveness endpoint is the composite endpoint of ischemic stroke or systemic embolism at 2 years.

Hypothesis:

$$H_0: p_e \geq PG_e$$

$$H_1: p_e < PG_e$$

where p_e is the event rate at 24 months. [REDACTED]

[REDACTED]

[REDACTED]

[REDACTED] The performance goal, PG_e is set at 9%, [REDACTED]

[REDACTED]

[REDACTED]

Analysis Methods:

[REDACTED]

Clinical Investigational Plan

Kaplan-Meier survival analysis will be used to estimate the event rate of at 24 months (731 days post implant). XXXXXXXXXX

Sample Size Determination:

A sample size of 257 subjects followed through 24 months will provide 80% power at the 2.5% significance level assuming a 24-month event rate of 4.5%. Assuming an attrition rate of 25% through 24 months, 343 subjects are required to be enrolled in the study.

Analysis Population:

Enrolled subjects who receive an implant of the ACP device will be included in the analysis.

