A study by Go et al. reviewed outcome data (11,526 patients) in a large primary care setting and confirmed that thromboembolic risk increases progressively with CHADS₂ score⁸. The study also noted that oral anticoagulation with warfarin reduces the risk of stroke in most patients with the exception of those at lowest risk (CHADS₂ score of zero) and highest risk (CHADS₂>5) for stroke. The more recently developed CHA₂DS₂-VASc risk assessment scheme⁹, which identifies truly low risk subjects, assigns two points to age \geq 75 years and previous stroke, TIA or thromboembolism and one point each to congestive heart failure or left ventricular dysfunction, hypertension, diabetes, vascular disease, age between 65-74 years and female sex. A recent validation¹⁰ of these risk schemes in more than 90,000 patients without oral anticoagulation (OAC) but on aspirin showed annual ischemic stroke rates ranging from 0.6% in CHA₂DS₂-VASc = 1 to 4.8% in CHA₂DS₂-VASc = 4, and more than 12% for CHA₂DS₂-VASc = 9.

Clinical Investigational Plan

In a meta-analysis conducted by Andersen et al., warfarin was found to be superior to aspirin and placebo in reducing the risk of systemic embolism in subjects with NVAF¹¹. Hart et al. reported that adjusted dose warfarin reduces stroke risk by 64% (6 trials) and antiplatelet agents reduce stroke risk by 22%¹². The study also reported that risk of intracranial hemorrhage was doubled with adjusted-dose warfarin compared with aspirin.

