5.2 STUDY DESIGN AND SCOPE

This is a prospective, multi-centre, single arm, post-approval observational study.

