5.2.3 Justification for study design

A single-arm observational study is appropriate to observe the safety and effectiveness of the ACP device in the post-market setting in China. The study includes a short-term safety endpoint, a long-term safety endpoint, and a long-term effectiveness endpoint.

The safety and effectiveness endpoints in this study are consistent with those reported for other studies or publications on left atrial appendage occlusion.

The short-term safety endpoint was chosen to reflect serious procedure-related complications during the implant procedure for the ACP device, resulting in either surgical or endovascular intervention. This endpoint appropriately captures important procedural complications and adequately characterizes the short-term safety profile of the procedure and the device.

The long-term safety endpoint is set at 24 months to capture long-term complications associated with the ACP device. This safety endpoint is based on the recently released EuroIntervention consensus document³⁴ on definitions, endpoints and data collection requirements for left atrial appendage occlusion clinical studies

Clinical Investigational Plan

Finally, the effectiveness endpoint appropriately reflects the occurrence of types of events (ischemic stroke or systemic embolism) that the device is intended to prevent. This endpoint is consistent with other studies and publications on left atrial appendage occlusion.

The performance goals for this study have been established primarily based on publications on the ACP device. Information has also been provided to support these performance goals based on outcomes with the WATCHMAN™ device.

Additional descriptive endpoints have been specified to characterize the mechanism of action of the device (i.e., device closure) and the long-term effects of device implant through 5 years.

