13.2 DESCRIPTIVE ENDPOINTS

The following endpoints will be summarized using descriptive statistics.

Rate of ischemic stroke or systemic embolism through 5 years post-implant:

Kaplan-Meier survival analysis will be used to estimate the rate of ischemic stroke or systemic embolism through 5 years post-implant. Subjects who receive an implant of the ACP device will be included in the analysis.

Occurrence of composite of damage to blood vessel or organ or damage to adjacent organs at implant, device dislodgement, device fracture, device erosion or pericardial tamponade through 5 years post-procedure :

Kaplan-Meier survival analysis will be used to estimate the rate of occurrence of the composite of device dislodgement, device fracture, device erosion, pericardial tamponade, damage to blood vessel or organ at implant access or damage to adjacent organs through 5 years post procedure. Subjects who receive an implant of the ACP device will be included in the analysis.

Device success rate- defined as device deployed and implanted in correct position:

The count and proportion of subject with device success will be summarized. Subjects who receive an implant of the ACP device will be included in the analysis.

Rate of closure of the LAA - defined as residual jet around the device of $\leq 5\text{mm}$, based on the 45-day TEE:

The count and proportion of subject with closure of the LAA will be summarized. Subjects who receive an implant of the ACP device will be included in the analysis.

Reporting:

The following data will be summarized and reported annually to CFDA.

- Investigator sites and enrollment status
- Demographic and baseline characteristics
- Serious Adverse events
- Protocol deviation

Clinical Investigational Plan

- Procedural results (procedure success, implanted device size, procedure duration)
- Device closure

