13.4 SUCCESS CRITERIA

The study has three primary endpoints for safety and effectiveness. All three endpoints must be met in order to declare success.

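### Does the fixed 9% two-year effectiveness goal need an observed/expected stroke analysis by CHA2DS2-VASc score before it can be interpreted?

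*Combined protocol and SAP*

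**What the plan says.** All references are to the combined protocol and SAP.

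- **Design (5.2).** "This is a prospective, multi-centre, single arm, post-approval observational study".
- **Goal (13.1.3).** "The performance goal, PG_e is set at 9" per cent. The null hypothesis is a 24-month rate at or above the goal. The analysis set is enrolled subjects who receive an implant, and the rate is estimated by Kaplan-Meier at 731 days.
- **Sample size (13.1.3).** 257 subjects followed through 24 months "will provide 80% power at the 2.5% significance level assuming a 24-month event rate of 4.5" per cent. With 25% attrition this becomes 343 enrolled.
- **Basis of the goals (5.2.3).** Primarily publications on this device, with WATCHMAN outcomes as support. The text beside the goal, parts of the analysis methods and most of 13.3 are redacted.
- **Choice of endpoint (5.2.3).** "the effectiveness endpoint appropriately reflects the occurrence of types of events (ischemic stroke or systemic embolism) that the device is intended to prevent".
- **Success (13.4).** "All three endpoints must be met in order to declare success".
- **Background risk (3.0).** Annual ischemic stroke rates of "0.6% in CHA₂DS₂-VASc = 1 to 4.8% in CHA₂DS₂-VASc = 4, and more than 12% for CHA₂DS₂-VASc = 9", in patients "without oral anticoagulation (OAC) but on aspirin".
- **Eligibility (4.1, 5.5.2).** CHA2DS2-VASc 0-1 and HAS-BLED below 3 are excluded. The population has a contraindication to long-term anticoagulation, or had a stroke or relevant event despite warfarin.
- **Reporting (1.0, 13.2).** The score and its components are collected at baseline, and "Demographic and baseline characteristics" are on the list for annual reporting.

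**The concern.** With no control arm, the only yardstick is 9%. The score-4 rate in section 3.0 corresponds to roughly 9% over two years, while scores 2 and 3 are also eligible and carry lower risk. If many such patients enrolled, their rate without any device could already be below 9%, and meeting the goal would say little about stroke prevention. Section 5.2.3 describes the endpoint in terms of what the device is meant to prevent, so a reader may well ask how the observed rate compares with the expected one. The score is collected, yet no readable text turns it into an expected number of events. If the plan used the 9% test as proof of stroke reduction against no device, a pass could be credited to the device when it was due to case mix.

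**Working it through.** **1. Reproduce the plan's figure.** Inputs from 13.1.3: goal 9%, assumed rate 4.5%, 80% power, 2.5% level (read as one-sided, since the alternative is a rate below the goal). With an exact binomial test, the smallest n with at least 80% power is 257:

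- P(X ≤ 14 | 257, 9%) = 0.0241 and P(X ≤ 15 | 257, 9%) = 0.0420, so a pass is 14 or fewer events (14/257 = 5.4%).
- Power: P(X ≤ 14 | 257, 4.5%) = 0.815.
- Enrolment: 257/0.75 = 342.7, rounded up to 343.

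The same method gives the plan's 231 for the 10% versus 5% safety endpoints. The binomial rule stands in for the Kaplan-Meier decision rule, which is not readable.

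**2. Chance that a device with no effect passes, by background two-year rate.** P(X ≤ 14 | 257, E):

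| E | P(pass) |
|---|---|
| 6% | 42% |
| 7% | 20% |
| 8% | 7.6% |
| 9% | 2.4% |
| 10% | 0.65% |

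This is the whole arithmetic content of the concern, and it is right. Score 4 gives 1 − (1 − 0.048)² = 9.4%; in a cohort made up entirely of score 4, P(pass) = 1.5%.

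**3. Which E is plausible?** The documents give rates only at scores 1, 4 and 9, so any mix needs an assumption. Two interpolations are used:

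- Linear: annual rate = 0.6% + 1.4% × (score − 1).
- Constant ratio between the quoted points, with score 9 taken as 12%.

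The two-year rate per score is 1 − (1 − r)². Scores are weighted equally within each mix.

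| Scores in mix | P(pass), linear | P(pass), constant ratio |
|---|---|---|
| 2-4 | 26% | 56% |
| 2-5 | 7.6% | 21% |
| 2-6 | 1.6% | 6.1% |
| 3-6 | 0.25% | 1.0% |
| 3-7 | 0.03% | 0.17% |
| 2-9 (all eligible) | 0.004% | 0.02% |

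The large figures come only from mixes anchored at score 2 and cut off at 4 or 5. The entry rules point the other way. A prior stroke alone scores 2 on CHA2DS2-VASc (7.1). HAS-BLED must be at least 3, and three of its items (hypertension, stroke history, age 65 or over) overlap with CHA2DS2-VASc items. This makes higher scores likely but does not guarantee them.

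**4. What does the plan claim from a pass?** Set side by side:

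- 5.1: the purpose is to observe safety and effectiveness after approval.
- 5.2.3: the goals come from device publications, so 9% is a benchmark against device experience.
- 5.2.3 on the endpoint: this explains why these event types were chosen. It does not compare with an untreated rate.
- 13.4: success means that the three goals are met, and nothing further is inferred.

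The 2.5% level applies to the stated null, a rate of 9% or more, and that error rate is held whatever the score mix.

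**5. What would an observed/expected analysis add?** Reference rates for scores 2, 3 and 5 to 8 are not in the documents. The reference patients took aspirin without anticoagulation, and the quoted rates cover ischemic stroke only. Study subjects' antithrombotic drugs are recorded at every visit (Table 2) and need not match, so a ratio below 1 could reflect drugs.

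Precision is also limited. If all 343 were implanted, with exponential attrition reaching 25% at 24 months, the attrition hazard is −ln(0.75)/2 = 0.1438 per year and exposure is 343 × 0.25/0.1438 ≈ 596 person-years. Counting only 257 completers gives 257 × 2 = 514. At a true 4.5% about 13 events are expected. The exact Poisson upper limit for 13 is 22.23, and 22.23/596 = 3.73% per year, or 1 − exp(−0.0746) = 7.2% over two years. The interval would exclude a ratio of 1 only if the expected two-year rate were above about 7.2%. It would often be inconclusive in the low-risk mixes that prompt the question.

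**The case for a change.** The best argument for the concern is that the addition is cheap and the question natural. The score is already collected, one paragraph would suffice, and fixing the reference rates in advance would prevent a later selective choice. Eligibility alone does not guarantee a background rate of 9% or more, and the same pass at 14 events lies 40% below an expected 9% (1 − 5.45/9) but only 9% below an expected 6% (1 − 5.45/6).

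The arithmetic stands, as does the caution that a pass at 9% should not by itself be read as proof of stroke reduction. The step from there to a fault in the plan does not. The readable plan makes no such claim, and a background-risk argument or supportive analysis may sit in the redacted text of 13.1.3 or 13.3, so its absence cannot be asserted. Nor is a background rate of 9% strictly needed: at a lower rate the data could still support a reduction if the upper confidence limit fell below that rate. Baseline characteristics are already due for reporting, so a reader who has the cited cohort's rates can make the comparison without changing the plan.

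**Conclusion.** The concern does not hold. The 9% test does what section 13.1.3 sets it up to do: the sample size reproduces exactly (257 evaluable, 343 enrolled), and the error rate against the stated null is 2.4%, within the 2.5% level. The probabilities that look alarming (20% at a 7% background, 42% at 6%) answer a different question, reduction against no device, which the readable plan does not pose. They also need a low-score cohort that the entry rules make unlikely. Mixes of scores 3-6, 3-7 or 2-9 give 1.0% or less under either interpolation.

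An observed/expected table would be a matter of preference, resting on a disputable external comparator. It would sit outside the success rule and alter no test, threshold, sample size or conclusion.

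This rests on three assumptions: the exact binomial as a stand-in for the Kaplan-Meier rule, interpolated rates for scores that the documents do not give, and the readable text alone. If a report later presented meeting 9% as proof of stroke reduction, the fault would lie in that reading of the result.
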